## **6 SAMPLE AND RECRUITMENT**

### **6.1 Eligibility Criteria**

Any patients that attend a specialist weight management service that has signed up to take part in this study will be eligible to be entered into this study.

#### **6.1.1 Inclusion criteria**

1. Patient is willing and able to give informed consent for the participation in the trial.
2. Over the age of 18.
3. Patient, in the investigator's opinion, is able and willing to comply with all the study requirements.
4. Patient is seen in a specialist weight management service across the England and Wales
5. Patient is willing and able to download an application in the English language

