#### SfE CORE Study Protocol

2. For the centres entering data to capture data on 60% of the patients attending their clinics.
3. To compare the data entered by 100 patients to that collected by a doctor in their initial interview. This will validate that data entry by patients is reliable.
4. To demonstrate that key outcomes are captured in sufficient quantity to give a fair representation of the people attending the clinics.
5. To describe the demographics and clinical characteristics of people attending the specialist weight management services who sign up to the study.
6. To look at changes in weight and well-being over the time in clinic and whether this is affected by treatment modality.
7. To explore potential disparities in access to specialist weight management services based on demographic factors (e.g., ethnicity, socioeconomic status).
8. To explore potential disparities in outcomes from specialist weight management services based on demographic factors (e.g., ethnicity, socioeconomic status).
9. To explore this methodology in collecting data on these characteristics from those patients who attend weight management services in primary care settings.

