### 3.2 Outcomes

	Objectives	Outcome Measures	Timepoint(s)
Primary	To demonstrate that our system can be integrated into specialist weight management services clinics and collect data on patients attending clinics.	The number of clinics using the system by end of year 2 of the project. Our aim would be to have 50% of specialist weight management services using this system.	24 months
Secondary	To demonstrate that key outcomes are captured in sufficient quantity to give a fair representation of the people attending the clinics	That the clinics on average are collecting data on 60% of the patients that attend their clinics and on these they have at least 80% data on our key outcomes which are  Demographics Age, sex, socioeconomic status, ethnicity, marital status and employment status and Job.	Baseline  Baseline

SfE CORE Study Protocol

		
Weight history Birth weight, age weight problem started at, highest and lowest weight. Current weight.
 
Previous Weight Loss Attempts Previous Bariatric surgery – Y/N – if Y when and Type. Attempts at commercial diets – Y/N if Y when and Type Tried weight loss medication – Y/N if Y when and Type
 
Medical and drug history List of medical problems with date started. List of drugs taking with dose, frequency and start date.
 
Clinical Treatments Diet and Exercise advice Y/N if yes details and date offered Low calorie diet Y/N if yes details and date started and finished. Specific help with eating habits Y/N, If yes details and date (S) delivered Sessions with psychologist Y/N, If yes details and date (s) delivered. Weight loss drugs Y/N if yes which type and when started. Referred for surgery Y/N if yes when.
 
Patient-Reported Outcomes EQ5D and Body Q
 
Clinical Measures Weight, height, BMI, blood pressure.
	
Baseline
 
Baseline and every 12 months until leaves clinic.
 
Baseline and every 12 months until leaves clinic.
 
Baseline and every 12 months until leaves clinic.
 
Baseline and every 12 months until leaves clinic.
 
Baseline and every 12 months until leaves clinic.
 
Baseline and every 12 months until leaves clinic.

--	--	---	---

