#### Data analysis

The primary outcome of this study is the number of clinics collecting data. Our aim is to get 50% of specialist weight management service using the database. We will report the number of specialist weight management service and what percentage of clinics are using the app at year 2 of the project.

The secondary outcomes of this study are the percentage of patients who we capture data on, and the percentage of data captured on key variables. Our aim to capture data on 60% of patients who attend the services and of those who sign up to the study aim to capture key data on 80% of these patients. The percentage of people we capture the data on will be = (the number of people we have data on/the number of people who attend the clinic) X 100. The percentage of key variable will be worked out for each variable and will be = (number of variable entered/ number of variable possible) x 100.

For the exploratory analysis we will use simple stats (mean, median, SD, interquartile ranges and percentage) to describe the demographic and clinical characteristics of the people entered into the database. Multivariable linear regression will be used to look at the change in weight, BMI, EQ5D and Body Q scores over 12 months and to determine if this is influenced by treatment modality and demographic groups. All analysis will be done in STATA.

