### **6.2 Sampling**

We will aim to recruit all patients who attend specialist weight management service in England and Wales (Scotland are exploring a different mechanism for collecting data from their specialist weight management service).

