### 6.2.2 Sampling technique

This will be convenience sampling with all patients attending the specialist weight management service offered to enter the study.

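### Inclusion criterion 3 lets investigators select on expected compliance, which could raise the 80% completeness result at the expense of the 60% capture result

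*Protocol*

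**What the plan says.** **Who is meant to enter.** Section 6.1 opens with: "Any patients that attend a specialist weight management service that has signed up to take part in this study will be eligible". Section 6.2 adds: "We will aim to recruit all patients who attend specialist weight management service in England and Wales". Section 6.2.2 describes a convenience sample with "all patients attending the specialist weight management service offered to enter the study".

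**The criterion.** Section 6.1.1 lists five inclusion criteria. The third requires that the "Patient, in the investigator's opinion, is able and willing to comply with all the study requirements". The other four cover consent, age, attendance at a service, and willingness and ability to download the English-language app. Section 6.1.2 excludes patients who cannot consent. The protocol does not define the study requirements that criterion 3 refers to. Sections 4 and 7.1 say there is no intervention, no extra visit and no change to routine, and section 7.6 lets patients enter their data at times of their own choosing.

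**The two targets.** Objective 4 in section 3.1 wants key outcomes "captured in sufficient quantity to give a fair representation of the people attending the clinics". Capture has a target of 60% and is defined under Data analysis in section 4 as "the number of people we have data on/the number of people who attend the clinic) X 100". Completeness has a target of 80% and applies to enrolled patients only: "of those who sign up to the study aim to capture key data on 80% of these patients" under Data analysis, and "on these they have at least 80% data on our key outcomes" in the table in section 3.2.

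**The concern.** In this study, complying means little more than supplying data, and how much data patients supply is what the completeness target measures. A gate on expected compliance therefore selects on something close to the endpoint itself. Criterion 3 is the only criterion that rests on a forecast of behaviour. Willingness is already covered by criteria 1 and 5, and capacity by the exclusion. With no definition of the requirements, each investigator has to set a personal threshold.

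If the gate is used and the forecasts are informative, completeness would look better than the system would achieve across all willing attenders. The same selection could reach the comparison of patient-entered with doctor-collected data in 100 patients (objective 3) and the descriptions of patients and their outcomes (objectives 5, 6 and 8). Section 6.2.1 ties adequate data collection to adoption of the system as the NHS standard, and routine use would include the patients whom the criterion allows sites to leave out.

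**Working it through.** **The plan's own figure.** The only computed figure in the sample section is projected enrolment: 700 × 1.5 + 700 × 2 = 2,450 per service; 2,450 × 0.80 = 1,960; 1,960 × 21 sites = 41,160. It reproduces exactly. It has no term for patients excluded under criterion 3, so it neither supports nor answers the point.

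**Inputs.** The targets (60% and 80%) and their denominators come from section 3.2 and Data analysis. The protocol gives no value for the following, so all are assumptions:

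- s, the share of would-be enrollees screened out under criterion 3: 5% to 30%
- cH, completeness in those kept: 85%
- cL, completeness that those screened out would have reached: 40% or 60%
- u, capture without screening: 60% for the table

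**Formulas.** Completeness without screening is (1 − s)cH + s·cL. With screening it is cH. The gain is s(cH − cL). Capture moves from u to u(1 − s).

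| s | Completeness without screening, cL = 40% | Gain (points) | Completeness without screening, cL = 60% | Gain (points) | Capture, from 60% |
|---|---|---|---|---|---|
| 5% | 82.75% | 2.25 | 83.75% | 1.25 | 57% |
| 10% | 80.5% | 4.5 | 82.5% | 2.5 | 54% |
| 20% | 76.0% | 9.0 | 80.0% | 5.0 | 48% |
| 30% | 71.5% | 13.5 | 77.5% | 7.5 | 42% |

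With screening, completeness is 85% in every row. If cL = cH, the gain is zero whatever s is.

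**Can screening turn a missed joint target into a met one?** Take 100 attenders of whom 75 are willing. Suppose 12 of them (16%) are screened out at cL = 40% and 63 are kept at 85%.

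- Without screening: capture 75%, completeness (63 × 85 + 12 × 40)/75 = 77.8%. The 80% target is missed.
- With screening: capture 63%, completeness 85%. Both targets are met.

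This needs two conditions at s = 16%. Capture must have slack: u must be at least 60/0.84 = 71.4%; at u = 70% capture falls to 58.8% and the site fails. The screened-out group must also be poor enough: cL below 85 − 5/0.16 = 53.75%. At cL = 60%, completeness without screening is (63 × 85 + 12 × 60)/75 = 81.0%, and the target is met without the criterion.

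**Data obtained per attender.** The product of capture and completeness falls by u·s·cL under screening. With u = 60%, s = 20% and cL = 40% it goes from 0.60 × 0.76 = 45.6% to 0.48 × 0.85 = 40.8%.

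**The case against.** A reader might infer that criterion 3 contradicts section 6.1 outright and that it inflates the completeness endpoint. The protocol does not support either in that form.

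- **Contradiction.** A general opening sentence followed by specific criteria is a common layout. Read literally, the opening sentence also conflicts with the consent, age and app criteria, to which nobody would object. Section 6.2.2 speaks of an offer to all, which is not the same as eligibility for all. This stands: it is a tension to reconcile.
- **Inflation.** Direction and size depend on how often the criterion is used and how well investigators predict completeness. The protocol is silent on both. Variation between sites is possible for the same reason, but not shown. This stands.
- **Counterweight.** Every patient screened out still counts in the capture denominator and lowers that result. The two targets are stated together in sections 3.2 and 6.2.1, so the pair is not inflated as a whole. This stands, subject to the slack condition above.
- **Staff entry.** Under Data collection in section 4, site staff check and correct patient entries and record measurements, HbA1c and treatments; registration has mandatory items with reminders. This limits the effect without removing it: EQ5D and BodyQ are key outcomes and come through the patient app (Appendix 2).
- **Little to act on.** With few real requirements, and with consent given in the app, screening before sign-up may be rare. Section 6.3.2, however, also lets investigators check and confirm each participant after consent, which is a second place where the criterion could be applied.

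**Conclusion.** The point holds as an avoidable selection route. Criterion 3 allows entry to depend on a forecast of behaviour close to what the completeness target measures, in a study that aims to represent all attenders. If used, it could bias completeness upward at the cost of capture. On the assumed ranges (cH = 85%, cL = 40% to 60%, s = 5% to 30%) the upward shift is about 1 to 14 points. It is zero if investigators do not predict completeness, and smaller in so far as staff supply the data. None of these inputs comes from the protocol, so no actual inflation is shown. The primary outcome, the number of clinics using the system, and the enrolment projection are untouched. Selection through consent and the English-language app remains whatever is done with criterion 3.

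**What to change.** Delete inclusion criterion 3. Keep the criteria on consent, age, attendance and the app, and the capacity exclusion. State in section 6.1.1 that expected non-compliance is not a reason to withhold the offer, and in section 6.3.2 that it is not a reason to reject a consented participant when the site validates entries. Reword the opening sentence of section 6.1 so that it refers to the criteria list.

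The cost is a short protocol amendment. Reported completeness may be slightly less favourable, by whatever the criterion would have added. Since the study involves no intervention and no extra visits, removing the criterion carries no safety cost.

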#### **6.1.2 Exclusion criteria**

1. Patients unable to give informed consent. This will be determined by the principle or sub investigator as to the patient's capacity at the time of informed consent.

### **6.2 Sampling**

We will aim to recruit all patients who attend specialist weight management service in England and Wales (Scotland are exploring a different mechanism for collecting data from their specialist weight management service).

#### **6.2.1 Size of sample**

We have not conducted a formal power calculation for this study. The primary objective is to evaluate whether this database can collect sufficient data from specialist weight management service to develop a national profile of patients attending these clinics, the treatments provided, and the effectiveness of these treatments. Previous efforts to collect data from these clinics have been limited

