**SfE CORE Study Protocol**

**ROLES AND RESPONSIBILITIES OF STUDY MANAGEMENT COMMITTEES/GROUPS & INDIVIDUALS**

On this project there will be a Study steering committee and patient and public involvement group.

The study steering committee, chaired by a Consultant Endocrinologist, will meet up to 3-4 times a year to:

- Suggest any changes to the data being collected (which if made will be made after ethical approval).
- Suggest sites which would be suitable to participate in the collation of data
- Sign off on the yearly annual report.
- Determine who is able to have access to the anonymised data generated by the Database
- Consider whether additional projects can be tied to this database.
- Oversee the management of the budget for the project provided by external funders, held at the Society for Endocrinology

The patient and public involvement group will meet two times a year to:

- Suggest any changes to the data being collected or the way in which we do this if patients are describing difficulty with using the app (which will only be after ethical approval).
- Suggest what changes could be made to our method of recruitment if we are struggling to engage patients.
- Help with news letters to patients involved in the study.
- Comment on the yearly annual report.
- Comment on any results that are obtained.
- Help with publications and producing literature explaining the results of the study to patients and the public.

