### 1 BACKGROUND

Obesity is an escalating issue in the UK, which currently has the highest obesity rate in Europe [1]. Approximately 27% of the adult population is classified as obese, contributing significantly to the primary care workload, with obesity associated with 44% of Type 2 diabetes cases, 23% of ischaemic heart disease cases, and 41% of certain cancer types [2]. Notably, the prevalence of severe obesity—an important factor in reduced life expectancy—has doubled over the past decade, affecting approximately 2.6 million adults [2].

The current framework for obesity management in the UK consists of a four-tier model. Tier 1 focuses on prevention and is managed by Public Health initiatives. Tier 2 services are community-based, providing referrals to evidence-based lifestyle interventions such as Weight Watchers and the Counterweight Programme. Individuals in Tier 2 typically have a BMI of 28-35 and do not present with complex medical issues. Tier 3 services or specialist weight management services represent a multidisciplinary specialist approach, available in community, primary or secondary care settings. This tier caters to individuals with a BMI greater than 35 (or over 30 if they have diabetes) and complex medical conditions, offering pharmacotherapy, low-energy liquid diets, and pre- and post-bariatric surgery care. Tier 4 services, located within secondary care, focus on bariatric surgery.

Data on obesity rates are systematically collected by the National Audit Office, enabling monitoring of Tier 1 effectiveness. Additionally, the National Bariatric Database provides insights into bariatric surgery rates, patient characteristics, and surgical outcomes [3]. However, comprehensive data on Tier 3 or specialist weight management services remain scarce, with information primarily available from only 4 of the 42 tier 3 clinics. Consequently, it is challenging to ascertain the availability of Tier 3 services across different regions, the volume of referrals, the demographics of individuals accessing these services, and their outcomes during treatment. This lack of data hinders our ability to evaluate equitable access, appropriate referrals, and the overall effectiveness of these services throughout the UK.

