#### SfE CORE Study Protocol

in scope, falling short of achieving a comprehensive national overview. Should this project succeed in gathering adequate data, this system will be commissioned as the NHS-standard platform for such data collection.

Our target is to engage 50% of specialist weight management service to use this system and capture 80% of essential data points for 60% of patients attending these clinics. Each weight management service typically receives approximately 700 patient referrals annually, with patients spending an average of 18 months in the program. We plan to recruit patients for two years, tracking outcomes for the duration of their clinic attendance. Data entry can be retrospective, allowing us in the first year to gather data on approximately 1,050 existing patients ( $700 \times 1.5$ ) and 700 newly referred patients each in the first and second years, leading to a potential recruitment of 2,450 patients per service.

Assuming an 80% capture rate, we anticipate enrolling 1,960 patients per clinic, resulting in a total of 41,160 patients across 21 participating sites.

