**Approvals :** Following Sponsor approval, the protocol, informed consent form, participant information sheet will be submitted to an appropriate Research Ethics Committee (REC), HRA and NRSPCC (Scotland only) (where required), and host institution(s) for written approval. The Investigator will submit and, where necessary, obtain approval from the above parties for all substantial amendments to the original approved documents.

**Other Ethical Considerations:** Data will be sourced from secondary care institutions or electronic data capture systems.

**Reporting:** The CI shall submit once a year throughout the clinical trial, or on request, an Annual Progress Report to the REC, HRA (where required), host organisation, funder (where required) and Sponsor. In addition, an End of Trial notification and final report will be submitted to the REC, host organisation and Sponsor.

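### The success thresholds cannot show that a nation, region or care setting is missing, yet they are the only visible test of whether the data support a national profile

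*Protocol*

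**What the plan says.** Section 6.2.1 describes the primary objective as "to evaluate whether this database can collect sufficient data from specialist weight management service to develop a national profile of patients attending these clinics", together with the treatments given and how well they work. Section 6.2 sets the population: "We will aim to recruit all patients who attend specialist weight management service in England and Wales".

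Success is judged by three thresholds, brought together in Section 6.2.1: "Our target is to engage 50% of specialist weight management service to use this system and capture 80% of essential data points", with patient capture set at 60%. Section 3.2 makes the service count the primary outcome at 24 months: "Our aim would be to have 50% of specialist weight management services using this system". The analysis in Section 4 matches it: "We will report the number of specialist weight management service and what percentage of clinics are using the app at year 2 of the project". Section 3.2 also has a secondary outcome, which takes 60% patient capture, averaged over clinics, and at least 80% key-data completeness as showing that attenders are fairly represented.

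Services sign up voluntarily (Section 6.1), and one task of the steering committee is to "Suggest sites which would be suitable to participate in the collation of data". The visible text sets no minimum by nation, region or care setting, plans no breakdown of uptake by these features, and plans no comparison of joined with non-joined services.

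**The concern.** The stated purpose is about whom the data represent, but the thresholds measure only how much is collected. A total of half the services says nothing about which half. The 60% and 80% figures describe patients and data within joined services, so they carry no information about services that stayed out.

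This touches the study's own reasons for existing. Section 1 complains that regional availability and equity of access cannot be judged, and places specialist services in several settings: "available in community, primary or secondary care settings". Section 2 promises to say whether effectiveness differs between areas. All three thresholds could be met with those questions unanswered for a whole area or setting, and the result could still be presented as a national profile. A large sample would make such a profile look precise without making it more representative.

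**Working it through.** **Inputs.** About 49 services (Section 1, Study Aim); 50%, 60% and 80% thresholds (Sections 3.2, 4 and 6.2.1); 700 referrals a year, 18 months' average stay and 21 sites (Section 6.2.1).

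**1. The plan's own figure.** Per service: 700 × 1.5 + 700 + 700 = 2,450. At the 80% capture used there: 2,450 × 0.80 = 1,960. Over 21 sites: 1,960 × 21 = 41,160. This reproduces exactly. Note that 21 is half of the 42 clinics mentioned in Section 1, but 21/49 = 42.9% of 49, and that the 80% differs from the 60% patient target. At 60% and 25 services the figure would be 2,450 × 0.60 × 25 = 36,750.

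**2. How many services may be absent.** 0.50 × 49 = 24.5, so 25 services meet the target and 49 − 25 = 24 may be missing. Any nation, region or setting holding up to 24 services can be wholly absent with the primary target met.

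**3. Share of attenders covered at the thresholds**, if services are of equal size: 25/49 × 0.60 = 30.6%.

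**4. What each threshold can detect.**
- 50% of services: a pooled count, unchanged by where the joined services are.
- 60% of patients: an average over joined clinics; a service outside the study does not enter it.
- 80% of key data: computed variable by variable on enrolled patients; again blind to services outside.

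**5. Size of the possible error.** Let f be the share of attenders in joined services and D the joined minus non-joined difference in some percentage. Even with perfect capture inside joined services, the profile differs from the national value by (1 − f) × D. With equal-sized services and 25 joined, 1 − f = 24/49 = 0.49. The documents give no D, so a range is assumed:
- D = 5 points: 0.49 × 5 = 2.4 points
- D = 10 points: 0.49 × 10 = 4.9 points
- D = 20 points: 0.49 × 20 = 9.8 points

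With the 21 sites of Section 6.2.1 the factor is 28/49 = 0.57.

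**6. Comparison with sampling error.** For an assumed prevalence of 40% and n = 36,750, ignoring clustering, the 95% half-width is 1.96 × √(0.4 × 0.6 / 36,750) = 0.5 point. The error in step 5 does not shrink as enrolment within joined services grows.

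**The case against.** The strongest reply is that this is a proof of concept for a data collection system. The protocol openly declares convenience sampling in Section 6.2.2, objective 5 in Section 3.1 limits description to people who sign up, and Section 6.2.1 asks only whether a national profile could be developed. On that view, stratified coverage is a preference, and breakdowns and weights belong in a statistical analysis plan, which is not shown. Also, the text of Section 5 (Study setting), listed in the contents, was not available here; a rule on site spread could stand there.

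Much of this stands. The Section 5 caveat is real and should be checked first. Weighting is an analysis detail, and weights cannot fill an empty stratum. What does not fall away is that the protocol itself fixes the success criteria and the claim they are meant to support. Section 3.2 treats meeting the capture and completeness thresholds as evidence of fair representation. That pairing is a protocol matter.

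Several stronger readings are tempting but unsupported.
- A reader might infer that success rests on one count. It does not: patient capture and completeness are also required.
- A reader might infer that commissioning follows from reaching 50%. Section 6.2.1 ties it to adequate data, which it does not define, so the link is an inference.
- A reader might take "Data will be sourced from secondary care institutions or electronic data capture systems" in Section 7 as restricting the study to secondary care, against Section 1. The sentence offers electronic data capture as an alternative source, and Section 6.3.1 names both secondary and primary care sites, so there is no contradiction.
- A reader might attach a probability to Wales being left out. The number of Welsh services is not given, so no such figure can be supported.

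**Conclusion.** The point holds as a limit on what the stated thresholds can show. Meeting all three would not establish that the data support a national profile of England and Wales, because none responds to an absent nation, region or setting, or to differences between services that opt in and those that do not. At the minimum, 24 of 49 services are unobserved, and the resulting error is about 0.49 × D.

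This rests on about 49 services, on services of equal size, and on a D that the documents do not supply. It would be wrong to conclude that the profile is biased: if joined and non-joined services are alike, D is near zero and nothing is lost. Nor does the setting point extend to general primary care, which Section 1 leaves to a second phase; it concerns specialist services in their different settings. The conclusion is also conditional on Section 5 containing no rule on site spread. The change is worth making because it is cheap and bears directly on what the study may claim.

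**What to change.** In Sections 3.2, 4 and 6.2.1:
- Keep the 50% target as it is.
- At month 24, also report joined over total services by nation, region and setting of the specialist service. Use the directory that supplies the denominator (reference 4), supplemented if it lacks these fields.
- Call the profile *national* only if every nation, region and setting has joined services. Otherwise describe the population as participating services.
- Weighting to the distribution of services over coarse, filled strata may be added, as a sensitivity analysis only.

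If Section 5 already has a rule on site spread, refer to it in these sections instead of adding a second one.

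The cost is protocol wording and one table, with some effort if the directory has to be supplemented. No extra patients are needed. The downside is that the success claim may become narrower.
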